# 9.1.2 Caregiver of a Pediatric Patient Survey

For each of the primary objectives of the Caregiver of a Pediatric Patient Survey, data will be analyzed based on the total sample and each subgroup:

- Country
- HAE Type
- Age (categorical: <12 years, and 12-17 years)

- Number of angioedema attacks in the past 6 months (0 attacks, 1-3 attacks, 4-6 attacks, 7-12 attacks, ≥13 attacks)
- On-Demand Treatment Status (Currently using on-demand treatment vs. no on-demand treatment)
- Prophylactic treatment status [Currently on a long-term prophylactic treatment (in total and broken out by prophylactic type) vs. not currently on a long-term prophylactic treatment]

Objective 1: To describe pediatric HAE patient characteristics, including demographics and clinical characteristics overall and separately for each subgroup.

Appropriate descriptive summary statistics (e.g. mean and SD, median and
interquartile range) will be presented for patient characteristics overall and for
each subgroup. Demographic characteristics will include age and sex. Clinical
characteristics will include HAE type, age at onset and diagnosis, doctors seen for
diagnosis; time, duration, and location of the most recent angioedema attack.

Objective 2: To describe the caregiver perspective on the humanistic burden of HAE on both pediatric patients and caregivers overall and for each subgroup.

• Appropriate descriptive statistics will be presented for survey items related to patient and caregiver impacts. The data will be presented overall and within each subgroup as relevant.

Objective 3: To describe the economic burden associated with HAE as experienced by caregivers of pediatric patients including the direct costs of illness and work absenteeism overall and for each subgroup.

Appropriate descriptive statistics will be presented for survey items related to
costs of illness and impacts on work. The data will be provided overall as well as
within each subgroup.

# 9.1.3 Caregiver of an Adult Patient Survey

For each of the primary objectives of the Caregiver of an Adult Patient Survey, data will be analyzed based on the total sample and each subgroup:

- Country
- HAE Type
- Number of angioedema attacks in the past 6 months (0 attacks, 1-3 attacks, 4-6 attacks, 7-12 attacks, ≥13 attacks)
- On-Demand Treatment Status (Currently using on-demand treatment vs. no on-demand treatment)
- Prophylactic treatment status [Currently on a long-term prophylactic treatment (in total and broken out by prophylactic type) vs. not currently on a long-term prophylactic treatment]

Objective 1: To describe the humanistic burden of caregiving for an adult HAE patient overall and for each subgroup.

 Appropriate descriptive statistics will be presented for survey items related to caregiver impacts. The data will be presented overall and within each subgroup as relevant.

Objective 2: To describe the economic burden associated with HAE as experienced by caregivers of adult patients including the direct costs of illness and work productivity and absenteeism overall and for each subgroup.

 Appropriate descriptive statistics will be presented for survey items related to costs of illness and impacts on work. The data will be provided overall as well as within each subgroup.

#### 9.1.4 Analysis Plan for Secondary Objective(s)

Secondary Objective 1: To assess the relationship between HAE control and number of attacks, on HRQoL and emotional well-being among adult HAE patients.

• Regression models will be used to assess the relationship between AECT scores and number of HAE attacks on HRQoL (AE-QoL scores and SF-12 component summary scores) and emotional well-being (HADS emotional distress subscale score). The dependent variables will be AE-QoL scores and SF-12 component summary scores (in separate models) and the independent variables will be AECT scores or number of attacks. The model will also include covariates to control for background characteristics as appropriate.

Secondary Objective 2: To identify the demographic and clinical factors that impact quality of life and economic burden for patients with HAE among adult HAE patients.

• Multiple regression models using backwards stepwise selection and clinical relevance will be used to assess the demographic and clinical factors that are most important to PRO measure scores and the economic burden associated with HAE. The dependent variables, in separate models, will be the PRO measure scores (AE-QoL scores, SF-12 component summary scores and WPAI-GH scores) as well as direct cost of illness. The independent variables will include sex and clinical characteristics (including HAE type, long-term prophylaxis use, and long-term prophylaxis type) as appropriate.

#### 9.1.5 Sensitivity Analyses

Not applicable.

#### 9.2 Interim Analyses

No interim analyses are planned for this study.

#### 9.3 Determination of Sample Size

For the main patient survey, a minimum sample size of 300 completed patient surveys is targeted. For each of the caregiver surveys (pediatric and adult), sample sizes of 250 and 200, respectively, are targeted.

In line with the objectives of the patient survey as well as recruitment feasibility assessments, the sample size of at least 300 participants may be considered sufficient to provide acceptable

levels of precision around the survey estimates (e.g.  $\pm 6\%$  around a sample proportion of 0.50) and to allow sufficient power (80%) to detect differences between groups of equal size, which are at least moderate in magnitude (identified as an effect size of 0.50 or greater). In line with the objectives and recruitment feasibility of the caregiver surveys, sample sizes of at least 100 participants are sufficient.

It can be seen in Table 7, a sample size of 100 individuals would give at minimum (i.e., around a proportion of 0.50) a precision of  $\pm 0.098$ , with a resulting CI width of at most 0.20 (0.40 to 0.60 around an estimate of 0.50). If the sample size increased to 200 individuals the precision would increase to a minimum of  $\pm 0.069$ , with a resulting CI width of at most 0.14 (0.43 to 0.57 around an estimate of 0.50). Importantly, the increasing precision around samples of increasing size has the greatest impact up to a sample size of 400; sample sizes of 500 and 600 provide additional precision for the additional sample size, with the precision increasing only from 0.049 to 0.043 with an increase from 400 to 500, and from 0.043 to 0.039 from 500 to 600.

Table 7: Sample Size Calculations (Whole sample)

Sample size:	100	200	300	400	500	600		
	Estimated	Estimated proportion $= 0.50$						
Precision±	.098	.069	.056	.049	.043	.039		
95% CI	.4060	.4357	.4456	.4555	.4554	.4654		
Width of 95% CI	.196	.138	.112	.098	.086	.078		
	Estimated	Estimated proportion = 0.25						
Precision±	.085	.069	.049	.042	.038	.034		
95% CI	.1734	.1832	.2030	.2129	.2129	.2229		
Width of 95% CI	.170	.138	.098	.084	.076	.068		

In terms of the precision of smaller groups of patients, such as those by country, the implications for varying sample sizes in terms of estimates of proportion are shown in Table 8.

Table 8. Sample Size Calculations (By country)

Sample size:	10	20	30	40	50	60	70	80	90	100
	Estimated proportion = 0.50									
Precision±	.31	.22	.18	.155	.139	.127	.117	.110	.103	.098
95% CI	.19-	.28-	.32-	.35-	.36-	.37-	.38-	.39-	.40-	.40-
	.81	.72	.68	.66	.64	.63	.62	.61	.60	.60
Width of 95%	.62	.44	.36	.31	.278	.254	.235	.22	.207	.196
				Estim	ated prop	ortion = (	).25			
Precision±	.270	.190	.155	.135	.121	.110	.102	.095	.089	.085
95% CI	02-	.06-	.10-	.12-	.13-	.14-	.15-	.16-	.16-	.17-
	.52	.44	.41	.39	.37	.36	.35	.35	.34	.34
Width of 95%	.54	.38	.31	.27	.242	.22	.204	.19	.179	.170

These values indicate that for a sample with 20 participants, the precision around a sample estimate of 50% would be  $\pm 22\%$ , meaning that (with 95% confidence) the true value in the population could lie anywhere from 28% to 72%. It thus would be difficult to draw meaningful conclusions from data obtained from such a small sample. The precision increases with the increasing number of participants, with the precision being  $\pm 10\%$  for a sample size of 70 and a sample estimate of 25%, meaning that the true value could lie anywhere from 15% to 35% (i.e., overall width of CI=20%). This level of precision is still fairly low and will be unlikely to provide much scope, unless the effect size is large, for claiming any statistically significant group level differences.

#### 9.4 Bias and Confounding

Selection bias may exist due to the route of recruitment via medical societies and patient associations. The survey will also rely on self-reported, retrospective data, which has the potential for recall bias [Bygum, et al., 2012].

# 9.5 Missing Data

No missing data are expected from the online survey data source up until the point when the participant either completes the survey or stops completing it before the survey end. The

questionnaires will be scored according to the developers' guidelines; and missing data will be handled accordingly. The frequency of any such missing data will be presented. No imputation of any missing data will be undertaken.

# 9.6 Significance Levels and Multiplicity

This is an observational survey study and findings are descriptive in nature. The study does not impose a therapy protocol, diagnostic/therapeutic procedure, or a visit schedule. Participants will complete one-time, web-based survey. An internet protocol (IP) blocker will be incorporated in the survey in order to avoid multiple responses from the same participant.

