# **6.2.2** Caregiver of a Pediatric Patient Survey

The Caregiver of a Pediatric Patient Survey study will target up to 250 caregivers of children and adolescents (≤ 17 years old) with a diagnosis of HAE (type I, II, normal functioning C1-INH, and unknown) in the following countries: Argentina, Brazil, Colombia, Croatia, Denmark, Hungary, Ireland, Norway, Poland, Portugal, Romania, and Sweden. If a caregiver of a pediatric patient is also an HAE patient themselves, they will be able to complete both the patient survey and the caregiver of a pediatric patient survey.

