# **6.2.3** Caregiver of an Adult Patient Survey

The Caregiver of an Adult Patient Survey study will target up to 200 caregivers of adults (≥ 18 years old) with a diagnosis of HAE (type I, II, normal functioning C1-INH, and unknown) in the following countries: Argentina, Brazil, Colombia, Croatia, Denmark, Hungary, Ireland, Norway, Poland, Portugal, Romania, and Sweden. If a caregiver of an adult patient is also an HAE patient, they will be able to complete both the patient survey and the caregiver of an adult patient survey. Caregivers of adults will be recruited through adult participants who take the survey. The adult participant will be asked if they have a caregiver they would like to refer to the study, and be provided with a unique link to send to their caregiver. In this way, the responses of the adult patient and their caregiver can be compared.

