#### **6.3.4** Schedule of Assessments

This is an observational study and does not impose a therapy protocol, diagnostic/therapeutic procedure, or a visit schedule. The surveys are one-time, web-based surveys. The HAE Patient Survey is expected to take 45-minutes, the Caregiver of a Pediatric Patient Survey is expected to take 30-minutes, while the Caregiver of an Adult Patient Survey is expected to take 20-minutes.

Caregivers with more than one child with HAE are able to complete the Caregiver of a Pediatric Patient Survey more than once. Caregivers with more than one child will be instructed to complete entire survey with the eldest child in mind. Upon completion of the survey, the caregiver will be provided with a unique link. The link will lead to an abridged version of the survey that will only include the following sections:

- Patient Information
- Patient's Most Recent Angioedema
- Impact of HAE on Child/Adolescent Patient

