## 6.6.5 Participant Completion of the Study

Participants should be included in the study only once. Data erroneously collected from participants without electronic consent will not be included in or will be deleted from the database.

A survey is considered completed if the participant answered all required questions. The survey will not progress unless a response is provided to a required question. Upon completion of the survey, the participant will be provided with a unique completion code. The participant will email the completion code to their country-specific patient advocacy, professional organization, medical society, or healthcare provider (Ireland and Portugal), which will then confirm the code with ICON. Upon confirmation, the patient advocacy organization, medical society, or healthcare providers will remunerate participants for the completion of the survey, per the following:

- HAE Patient Survey: An equivalent of \$45 USD
- Caregiver of a Pediatric Patient Survey
  - o First completion: An equivalent of \$30 USD
  - Subsequent completions: An equivalent of \$15 USD
- Caregiver of an Adult Patient Survey: An equivalent of \$30 USD

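### The IP blocker in section 9.6 works on connections, not people, and the only-once wording contradicts the repeat and dual completions that the protocol permits

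*Protocol*

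**What the plan says.** Section 9.6 sets the control on duplicates: "An internet protocol (IP) blocker will be incorporated in the survey in order to avoid multiple responses from the same participant". The sentence just before it reads "Participants will complete one-time, web-based survey". Section 6.6.5 adds "Participants should be included in the study only once". None of these carries an exception.

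Other sections invite more than one completion per person:

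- Section 6.2.2, on a pediatric caregiver who also has HAE: "they will be able to complete both the patient survey and the caregiver of a pediatric patient survey".
- Section 6.2.3, on an adult's caregiver who also has HAE: "they will be able to complete both the patient survey and the caregiver of an adult patient survey".
- Section 6.3.4: "Caregivers with more than one child with HAE are able to complete the Caregiver of a Pediatric Patient Survey more than once". The later report is an abridged form reached by its own link.
- Section 6.6.5 itself sets a USD 15 payment for second and later pediatric caregiver completions.

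Several respondents per household are also expected. Section 6.2.3 says "Caregivers of adults will be recruited through adult participants who take the survey", and the patient will "be provided with a unique link to send to their caregiver". Tables 4 and 5 record whether caregiver and patient live together and how many household members have HAE.

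**The concern.** The blocker is meant to stop one person answering twice, but it acts on the network address. In a hereditary disease, two affected adults behind one home router are an ordinary case, and to an IP filter they look like one person answering twice. A patient and the caregiver whom that patient refers are another pair likely to share a connection.

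Two things are at stake. First, whoever builds the survey must choose between instructions that cannot all be followed: one completion only, or the second completions that other sections permit and pay for. Second, if genuine respondents are turned away, the loss depends on household composition. That may be related to caregiving burden, which is a primary objective. Section 9.4 lists bias from the recruitment route and from recall, but not this. Respondents rejected during fielding cannot be recovered at analysis.

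**Working it through.** **Step 1. The completion rules side by side.**

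| Situation | 9.6 and first sentence of 6.6.5 | Elsewhere |
|---|---|---|
| Patient who also cares for a child with HAE | one completion | two allowed (6.2.2) |
| Patient who also cares for an adult with HAE | one completion | two allowed (6.2.3) |
| Caregiver with two or more affected children | one completion | repeats allowed (6.3.4) and paid (6.6.5) |

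The two columns cannot both be followed. The payment clause shows that repeats are intended, so the restrictive sentences are the ones to reword.

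**Step 2. What the blocker does under each possible scope.** The protocol does not say whether it acts within each survey, per link or across all surveys. Assume both responses come over one connection.

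| Second response | Own link? | Block within each survey | Block across all surveys |
|---|---|---|---|
| Second affected adult, patient survey | no; the link is advertised (6.6.1) | rejected | rejected |
| Referred adult caregiver living with the patient | yes (6.2.3) | accepted | rejected unless the link is exempt |
| Patient who is also a caregiver | different survey | accepted | rejected unless exempt |
| Later-child report | yes, abridged form (6.3.4) | depends on whether the form counts as the same survey | rejected unless the link is exempt |

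Only the first row is rejected under both scopes. The other three depend on a setting that the protocol does not give.

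**Step 3. The plan's own precision figure.** No figure in the protocol depends on the blocker. The nearest is the 95% half-width in Table 7, 1.96 × √(p(1−p)/n) at p = 0.50:

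- n = 100: 0.098, as stated.
- n = 200: 0.069, as stated.
- n = 250: 0.062 (not in the table).

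**Step 4. Illustrative size, on assumed inputs.** Let s be the share of invited caregivers on the patient's IP address, f the fraction of those who are blocked, and d the difference in an outcome proportion between shared-IP and other caregivers. None of the three is in the protocol. Then:

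- number remaining = N(1 − s·f)
- observed shared-IP share s′ = s(1−f) / [s(1−f) + 1 − s]
- bias = (s′ − s)·d

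With N = 200, the adult-caregiver target in section 9.3, and d = 0.10 to 0.20:

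| s | f | Remaining | s′ | Absolute bias, points |
|---|---|---|---|---|
| any | 0 | 200 | s | 0 |
| 0.3 | 0.5 | 170 | 0.176 | 1.2 to 2.5 |
| 0.5 | 0.5 | 150 | 0.333 | 1.7 to 3.3 |
| 0.7 | 0.5 | 130 | 0.538 | 1.6 to 3.2 |
| 0.3 | 1 | 140 | 0 | 3 to 6 |
| 0.5 | 1 | 100 | 0 | 5 to 10 |
| 0.7 | 1 | 60 | 0 | 7 to 14 |

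Section 9.3 calls 100 caregivers sufficient. Falling below that needs more than 1 − 100/200 = 50% of the adult-caregiver target to be lost, or more than 1 − 100/250 = 60% of the pediatric one.

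**The case against.** The strongest reply is that the blocker's scope is unstated and a sensible build would avoid most of the harm. The three surveys are separate, participants enter by their respective links, and adult-caregiver and later-child responses have unique links. If those routes lie outside the block, loss and bias on them are zero. People can also answer from different networks. The payment for later completions makes the intent plain, so the contradiction could be called a wording slip.

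Much of this stands. A reader might infer that the blocker does lock out caregivers and that their data are lost selectively. The protocol does not establish that. Four other inferences also fail:

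- **That sibling reports are analysed as independent records, so precision is overstated.** No section says so. Section 9.1.2 plans descriptive summaries, and the regressions in 9.1.4 concern adult patients. Caregiver outcomes are collected once per caregiver anyway, because the abridged form omits those sections.
- **That real duplicates go unchecked.** A repeat from another network would pass an IP filter, but section 6.6.5 requires a completion code to be confirmed before payment. That gates payment rather than data entry, yet it weakens the incentive.
- **That reaching 200 adult caregivers leaves no slack.** The ratios 200/394 = 51% and 200/300 = 67% are referral rates and do not measure blocking. The target is also an upper limit, with 100 called sufficient.
- **That blocked caregivers carry the highest burden.** This is plausible, but nothing in the protocol shows it.

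The reply does not cover the second affected adult on the patient survey, who has no unique link and is rejected even by a block confined to that survey. Nor does it reconcile the completion rules.

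**Conclusion.** The point holds in a limited form. The contradiction between the only-once wording and the permitted second completions is certain on the text. The rejection of a second affected adult in one household follows from the blocker as written, given only that both answer over the same connection. The possible loss is therefore not confined to caregiver data. Loss of co-resident caregivers, patient-caregivers and later-child reports is possible but conditional on configuration.

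The size cannot be computed from the protocol. In the illustration for adult caregivers, bias is zero if the linked routes are exempt, about 1 to 3 points if half of shared-IP caregivers are blocked, and 3 to 14 points if all are. These figures rest on assumed s of 0.3 to 0.7 and d of 0.10 to 0.20, and they are not an estimate of what will happen. The matter should be settled before fielding.

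**What to change.** 1. Reword 6.6.5 and 9.6 to one completion per person per survey and, for the pediatric caregiver survey, one per child.
2. Replace automatic IP rejection with a flag. Review same-IP records that also match on age, sex and country, and use the existing completion codes in that review. Alternatively, keep a block but confine it to each survey, exempt the unique-link routes, and provide a way in for a second patient in the household.
3. Report the number of records flagged or rejected, by survey.
4. State whether the pediatric target of 250 counts caregivers or completed surveys.

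The cost is a platform setting, a few sentences of protocol text and a short duplicate-review step. Flagging lets some suspect records in until review, so the review rule should be written before data collection starts.

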#### 10 Reports

A Non-Interventional Study Report based on the results obtained will be prepared and submitted to Takeda. The Final Study Report should be available within one year from collection of the last data point.

#### 11 Publication, Disclosure, and Clinical Trial Registration Policy

The Sponsor may have the results of this study published.

The Sponsor has the right to use the data and results for regulatory purposes and for internal presentation within the company and to partners.

# 12 Archiving of Study Documentation

During the course of the study, ICON must as a minimum file the below essential documents in the Study File:

- Written agreement between the Sponsor and ICON.
- The study protocol and any amendments
- Signed and dated protocol agreement and amendment agreements, if any, with the original signatures
- Informed consent forms in local language (notified to / approved by Independent Ethics Committees (IECs) / Institutional Review Boards (IRBs) as locally required)
- Written IEC / IRB approval / vote according to local regulations

In all scenarios, ICON will maintain source documents for each participant in the study, consisting of the screening questionnaire for 5 years. ICON will give Takeda (or designee) access to all relevant source documents to confirm their consistency.

# 14 Appendices

**Appendix A:** Recruitment Messages

**Appendix B**: Informed Consent Form

**Appendix C**: HAE Patient Survey

**Appendix D**: Caregiver of Pediatric Patient Survey

**Appendix E**: Caregiver of an Adult Patient Survey
